6.1.3. Analysis Methods

For assessments of the binary efficacy endpoints and binary health outcomes, proportions for each weight class/treatment group along with the 95% confidence intervals (CIs) using the Wilson Score method (Wilson 1927; Newcombe 1998) will be provided. Non-responder imputation method will be used to estimate the percentage of patients achieving response across post-baseline visits.

Assessments of the continuous endpoints, descriptive statistics (n, mean, standard deviation [SD], minimum, first quartile, median, third quartile, and maximum) will be provided for each specified visit. Where appropriate, the mean and mean change from baseline with corresponding 95% CIs will be presented at each specified visit.

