6.2. Adjustments for Covariates

This study is a multicenter, open-label PK study designed to evaluate the safety, PK, PD, and clinical response of mirikizumab in pediatric patients, and to provide data for dose confirmation for Phase 3. All patients will receive mirikizumab based on their baseline weight class for the Induction Period and Week 12 weight class for the Maintenance Period. Treatment comparisons are not planned to be performed, hence no adjustments for covariates will be warranted.

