	Each subscore is on a 4-point scale, ranging from 0 to 3.	PGA subscore	Possible values are: (0) Normal (1) Mild disease	Single item. Missing if missing.

Measure	Description	Variable	Derivation / Comment	Definition of Missing
			(2) Moderate disease	
			(3) Severe disease	
		Modified Mayo Score	Calculated as: SF + RB + ES.	Missing if SF, RB or ES
		(MMS)		subscores are missing.
		Partial Mayo Score	Calculated as: SF + RB + PGA.	Missing if SF, RB or PGA subscores are missing.
		Alternate MMS Clinical Remission	SF subscore = 0, or SF = 1 with a ≥1-point decrease from baseline, and RB subscore = 0, and ES subscore = 0 or 1 (excluding friability)	Missing if SF, RB, or ES subscores are missing.
		MMS Clinical	SF subscore = 0 or 1	Missing if SF, RB, or ES
		Remission	RB subscore $= 0$, and	subscores are missing.
			ES subscore = 0 or 1 (excluding friability)	J
		MMS Clinical Response	A decrease in the MMS of ≥2 points and ≥30% decrease from baseline, and A decrease of ≥1 point in the RB subscore from baseline or a RB score of 0 or 1	Missing if baseline or Week 12 MMS is missing.
		Endoscopic Remission	ES = 0 or 1 (excluding friability).	Missing if ES is missing.
		Symptomatic Remission	$SF = 0$, or $SF = 1$ with a ≥ 1 -point decrease from baseline and $RB = 0$	Missing if SF or RB is missing.
		Time to first symptomatic remission	For patients who are observed to meet the remission criteria during the Induction Period, time will be from the start of the Induction Period to the first measurement date where the patient met the remission criteria based on weekly averages.	Patients not observed to meet remission criteria during the Induction Period will be censored after the date of their last measurement during the Induction Period.

Measure	Description	Variable	Derivation / Comment	Definition of Missing
			CCI	
		Time to first symptomatic response	For patients who are observed to meet the response criteria during the Induction Period, time will be from the start of the Induction Period to the first measurement date where the patient met the response criteria based on weekly averages.	Patients not observed to meet response criteria during the Induction Period will be censored after the date of their last measurement during the Induction Period.
		Endoscopic subscore of 0	ES = 0.	Missing if ES is missing.
		Total Symptomatic Score	Calculated as SF + RB.	Missing if SF or RB is missing.

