Abbreviations: CFB change from baseline; CI = confidence interval; mBOCF = modified baseline observation carried forward; mITT = modified intent-to-treat; MMS = Modified Mayo Score; NRI = non-responder imputation; NRS = Numerical Rating Scale; PUCAI = Pediatric Ulcerative Colitis Activity Index; Q12W = every 12 weeks.

 Table AMBU.6.6.
 Description of Exploratory Efficacy/Health Outcomes Analyses

Measure	Variable	Analysis Method (Section 6.1.3)	Population (Section 6.1.1)	Time Point(s)
Mayo Score and components	Change from baseline in SF, RB, and Total Symptomatic Score	Descriptive statistics and 95% CI for mean with mBOCF and as observed.	mITT	At each scheduled visit
	Change from baseline in ES	Descriptive statistics and 95% CI for mean with mBOCF and as observed.	mITT	Weeks 12 and 52
	Time to first symptomatic response	Descriptive statistics and 95% CI for mean.	mITT	During Induction Period
	Time to first symptomatic remission	Descriptive statistics and 95% CI for mean.	mITT	During Induction Period
	MMS Alternative Clinical Remission	Proportion for each weight/treatment dose group along with the 95% 2-sided CI with NRI and as observed.	mITT	Weeks 12 and 52
CRP	CRP CFB	Descriptive statistics and 95% CI for mean with mBOCF and as observed.	mITT	Week 12 Week 52
Fecal calprotectin	Fecal calprotectin CFB	Descriptive statistics and 95% CI for mean with mBOCF and as observed.	mITT	Week 12 Week 52
PGIC	Mean PGIC Score	Descriptive statistics and 95% CI for mean as observed.	mITT	Week 4, Week 8, Week 12, and Week 52
PGRS	PGRS Score CFB	Descriptive statistics and 95% CI for mean with mBOCF and as observed.	mITT	At each scheduled visit.
Nocturnal Stool	Nocturnal Stool Score CFB	Descriptive statistics and 95% CI for mean with mBOCF and as observed.	mITT - In patients with a nocturnal stool score ≥1 at baseline	At each scheduled visit.
CCI				At each scheduled visit.
Bristol Stool Scale	Loose stool	Proportion for each weight/treatment dose group along with the 95% 2-sided CI with NRI and as observed	mITT, in patients with loose stool at baseline	At each scheduled visit.

		Analysis Method	Population	
Measure	Variable	(Section 6.1.3)	(Section 6.1.1)	Time Point(s)
EIMs	Resolution of Baseline EIMs	Proportion for each weight/treatment dose group along with the 95% 2-sided CI with NRI and as	mITT – in patients with EIMs at baseline	Weeks 12 and 52
		observed.		

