Appendix 1. Diary Calculations

Weekly summary measures of diary data will be created for each patient. The 7-day period associated with each week will be defined using a visit centric approach. The table below displays the interval for each week.

Week (Visit)	Start Day ^a	End Daya	
Screening	Max(Informed Consent Date, Week 0 Visit Date - 14)	Week 0 Visit Date – 8	
Baseline	Week 0 Visit Date – 7	Week 0 Visit Date – 1	
Week 2 (V3)	Max(Week 0 Visit Date, Week 2 Visit Date – 7)	Week 2 Visit Date – 1	
Week 4 (V4)	Max(Week 2 Visit Date, Week 4 Visit Date – 7)	Week 4 Visit Date – 1	
Week 8 (V5)	Max(Week 4 Visit Date, Week 8 Visit Date – 7)	Week 8 Visit Date – 1	
Week 12 (V6)	Max(Week 8 Visit Date, Week 12 Visit Date – 7)	Week 12 Visit Date – 1	
Continue the algorithm as above.			
Week 48 (V15)	Max(Week 44 Visit Date, Week 48 Visit Date – 7)	Week 48 Visit Date – 1	
Week 52 (V16)	Max(Week 48 Visit Date, Week 52 Visit Date – 7)	Week 52 Visit Date – 1	

a If End Day < Start Day, do not assign specified visit week. Visit date will be calculated by selecting the first date from the following list (ie, first in list order): (1) date of endoscopy preparation if endoscopy preparation was performed, (2) date of endoscopy if endoscopy was performed, (3) date of treatment if treatment was given,
 (4) office visit date if available, or (5) imputed date of visit center of the protocol-defined window for that visit.

For the Mayo SF and RB subscores, the most recent 3 nonmissing days of the 7-day period in the table above will be averaged and rounded to the nearest integer to calculate the weekly score for each patient. Patients with less than 3 measurements in the 7-day period will be considered missing.

All diary data collected on the following days will be excluded from any calculations:

- any day(s) of bowel preparation
- day after any day(s) of bowel preparation (will most often be associated with date of endoscopy)
- day of endoscopy
- day after endoscopy, and
- two days after endoscopy (patients will be answering questions in a 24-hour recall fashion, so two days following endoscopy, they may be reporting their patient-reported outcomes from the day after the endoscopy).

For the Bristol Stool Scale the worst (ie, maximum) of the available measures during the 7-period in the table above will be used to calculate a weekly score for each patient. If fewer than

4 days are available (ie, not missing), the patient will be considered to be missing data for that week.

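### Time to first symptomatic response and remission are right-censored, but the SAP summarises both by a mean with 95% CI and gives no method for censored times

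*SAP*

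**What the plan says.** SAP Table AMBU.6.4 (under Section 6.10.1) defines both times from the start of induction to the first measurement date on which the criterion is met. For remission: "Patients not observed to meet remission criteria during the Induction Period will be censored after the date of their last measurement". For response: "Patients not observed to meet response criteria during the Induction Period will be censored after the date of their last measurement". In both cases the last measurement is the last one in the Induction Period.

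The analysis is set in Table AMBU.6.6, for the mITT population over the Induction Period. The two rows read "Time to first symptomatic remission Descriptive statistics and 95% CI for mean" and "Time to first symptomatic response Descriptive statistics and 95% CI for mean". The method column of that table points to Section 6.1.3, where, for continuous endpoints, "descriptive statistics (n, mean, standard deviation [SD], minimum, first quartile, median, third quartile, and maximum) will be provided" by visit, with a CI for the mean where appropriate.

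**The concern.** For a censored patient the plan knows only that the time exceeds some value. Such a time cannot enter an ordinary mean, quartile or CI without a rule, and none is given. Two simple readings are open.

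- **Events only.** Patients who never meet the criterion are left out. The result describes achievers and says little about how many there were.
- **All patients, with censoring times entered as event times.** This equals the mean restricted to 12 weeks only if every non-achiever is followed to Week 12. A non-achiever who leaves at Week 4 contributes 4 weeks, so early loss looks like fast onset.

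The report could therefore carry either of two quite different mean times to response from the same data, and the choice could be made after the data are seen. The censoring rule itself is clear and is not questioned.

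**Working it through.** **Is a rule given elsewhere?** SAP Section 4.2 says where summary measures and missing-data handling are described. Those places, and the protocol, contain the following.

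| Place | Content | Rule for a censored time? |
|---|---|---|
| SAP 6.1.3 | Wilson intervals for proportions; ordinary descriptive statistics by visit | No |
| SAP 6.3, 6.3.1, 6.3.2 | NRI for categorical variables; mBOCF for visit values; observed-data analysis | No |
| SAP Table AMBU.6.4 | The censoring rule | Says who is censored, not how they are summarised |
| SAP Table AMBU.6.6, other readable rows | Each names NRI, mBOCF or observed data | Not applicable |
| Protocol 10.3.3.3 | Leaves exploratory methods to the SAP | No |

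Redaction does not explain the gap. The blacked-out cell near these rows is in the derivation column of Table AMBU.6.4, and both method cells in Table AMBU.6.6 are readable.

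**How far apart are the readings?** The plan states no figure for these endpoints, so there is nothing to reproduce first.

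Inputs:
- Assessment at Weeks 2, 4, 8 and 12, from SAP Appendix 1, where "The 7-day period associated with each week will be defined using a visit centric approach".
- Assumed: share *p* meeting the criterion by Week 12, from 0.3 to 0.9.
- Assumed: constant hazard, so F(t) = 1 − (1 − p)^(t/12).

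Let d_j be the increase in F at visit t_j.

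- Events-only mean = Σ d_j t_j / p
- Mean restricted to 12 weeks = Σ d_j t_j + 12(1 − p)

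For p = 0.5 the increments at Weeks 2, 4, 8 and 12 are 0.1091, 0.0972, 0.1637 and 0.1300, so Σ d_j t_j = 3.476. The events-only mean is 3.476/0.5 = 6.95 weeks. The restricted mean is 3.476 + 6 = 9.48 weeks.

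| p | Events-only mean (weeks) | Restricted mean (weeks) | Gap (weeks) |
|---|---|---|---|
| 0.3 | 7.30 | 10.59 | 3.29 |
| 0.5 | 6.95 | 9.48 | 2.52 |
| 0.7 | 6.44 | 8.11 | 1.67 |
| 0.9 | 5.42 | 6.08 | 0.66 |

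From p = 0.3 to 0.7 the events-only mean falls by 0.86 weeks (12%) and the restricted mean by 2.48 weeks (23%). The events-only mean thus responds about half as much in percentage terms, and about a third as much in weeks (0.86/2.48 = 0.35).

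The percentage contrast does not depend on constant hazard. With a Weibull shape of 0.6 the falls are 15% and 31%; with 1.6 they are 8% and 16%.

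**Effect of dropout at p = 0.5.** Assume that a share *q* leaves in equal thirds just after the Week 2, 4 or 8 measurement, independently of onset. Their expected entered times are 2.00, 3.78 and 6.96 weeks, averaging 4.25. The all-patients mean is then (1 − q) × 9.48 + q × 4.25.

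| q | All-patients mean (weeks) | Events-only mean (weeks) | Kaplan-Meier mean to Week 12 (weeks) |
|---|---|---|---|
| 0 | 9.48 | 6.95 | 9.48 |
| 0.05 | 9.22 | 6.88 | 9.48 |
| 0.10 | 8.95 | 6.81 | 9.48 |
| 0.20 | 8.43 | 6.65 | 9.48 |

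The last column is 2 + 2S(2) + 4S(4) + 4S(8) with S = 0.8909, 0.7937 and 0.6300. It does not move because dropout is assumed unrelated to outcome.

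**The case against.** The best defence is that the cell is under-specified rather than wrong. Writing that patients are censored suggests a time-to-event analysis was in mind, and descriptive statistics with a CI for the mean could be produced by a method that allows for censoring. The by-visit wording of Section 6.1.3 does not fit a once-per-patient time anyway, and its list includes a median. This is fair as to intent. But the cell sends the reader to a section holding only ordinary statistics, and no censoring-adjusted mean or median is named anywhere.

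The dropout effect is also small for this study. At p = 0.5 the SD of the restricted time is about 3.7 weeks, so with the roughly 10 patients planned above 40 kg (SAP Section 5.2) the standard error is about 3.7/√10 = 1.2 weeks. Dropout shifts of 0.26, 0.52 and 1.05 weeks lie below that. This stands. The 2.5-week gap between the two readings, about twice that standard error, is the stronger point.

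Finally, little depends on these endpoints. They are exploratory, and "Treatment comparisons are not planned to be performed". Symptomatic remission is also reported as a proportion at every scheduled visit (Table AMBU.6.5), and "Change from baseline in SF, RB, and Total Symptomatic Score" is summarised at each visit. This stands too, although no by-visit proportion is listed for symptomatic response.

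**Conclusion.** The concern holds, as a minor one. As written, the plan right-censors two times and then prescribes a summary that has no place for censored values. The two ordinary readings differ by 3.3 weeks if 30% of patients meet the criterion by Week 12 and by 0.7 weeks if 90% do. The share achieving, the hazard shape and the dropout pattern are all assumptions; the visit grid is the SAP's. That the method is missing rests on the text alone. The PK objective, the secondary endpoints and the efficacy analyses listed for the interim (SAP Section 6.16.2) are unaffected.

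**What to change.** In the two time-to-event rows of Table AMBU.6.6, replace the method with: *Kaplan-Meier cumulative percentage meeting the criterion by Weeks 2, 4, 8 and 12 with 95% CI, by weight/treatment dose group; median with CI where reached; numbers of events and of censored patients.* If a mean is kept, state that it is a Kaplan-Meier mean restricted to Week 12. Leave the censoring rule in Table AMBU.6.4 as it is.

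The cost is two table cells and minor programming on the same dataset, with no new data.

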6.3. Handling of Dropouts or Missing Data

Intercurrent events (FDA 2021) are events which occur after the treatment initiation and make it impossible to measure a variable or influence how it should be interpreted. Examples of such

events include treatment discontinuation due to death or adverse events (AEs), rescue treatment, and loss to follow-up. The missing data methods described below handle intercurrent events in different ways and thus are relevant to different estimands.

The Schedule of Activities outlined in the protocol specifies the allowable windows for assessments. Assessments performed outside these windows will not be excluded from any analysis, but will be reported as a protocol deviation (see Section 6.15). While every effort will be made to reduce missing data, the missing data imputation method of NRI will be used when patients are permanently discontinued from study drug or otherwise have missing data. For the "as observed" analysis, only data from completers at the visit are relevant, and therefore the analysis does not need to deal with missing data.

For any interim analyses that occur, patients who, based on their treatment start date, would not have completed the visit corresponding to the selected endpoint at the time of the database lock will not be included in the analysis of that endpoint unless otherwise specified. Patients who have discontinued or otherwise have missing data and would have otherwise completed that visit at the time of database lock will be counted as non-responders for the interim analysis. For example, if a patient who discontinued at Week 12 of the study would have been in Week 24 of the study at the time of database lock, would not be included in the analysis of endpoints at Week 36 or Week 52. If that same patient who discontinued would have been at Week 48 at the time of the interim database lock if they had remained in the study, they would be counted as a non responder for Week 36, but not included in the Week 52 analysis.

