6.3.1. Non-Responder Imputation (NRI)

For analysis of categorical efficacy and health outcomes variables, missing data will be imputed using an NRI method. Patients will be considered non-responders for the NRI analysis if they do not meet the categorical efficacy criteria or have missing clinical efficacy data at a time point of interest.

The NRI method may be used when the estimand of interest uses the composite strategy (FDA 2021) for handling intercurrent events. In this strategy, patients with any intercurrent events that lead to the permanent discontinuation of assigned study treatment are defined to have failed treatment for all subsequent time points.

In addition, patients who were not adequately assessed to determine if they meet the clinical requirements for response at the time point of interest are also considered to have failed treatment.

For any interim analyses that occur, patients who, based on their treatment start date, would not have completed the visit corresponding to the selected endpoint at the time of the database lock will not be included in the analysis of that endpoint. Patients who have discontinued or otherwise have missing data and would have otherwise completed that visit at the time of database lock will be counted as non-responders for the interim analysis.

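### Time to first symptomatic remission and response censors children who stop drug early at their last measurement, unlike the plan's failure rule elsewhere and with no stated strategy

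*SAP*

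**What the plan says.** SAP Table AMBU.6.4 (under Section 6.10.1) defines both variables in the same way. For remission, the event time runs from the start of induction to "the first measurement date where the patient met the remission criteria based on weekly averages". Children without the event are censored, and the row for response reads: "Patients not observed to meet response criteria during the Induction Period will be censored after the date of their last measurement during the Induction Period". The remission row has the same rule: those not observed to meet its criteria "will be censored after the date of their last measurement during the Induction Period". Neither row mentions stopping study drug.

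SAP Table AMBU.6.6 gives the analysis of both variables as descriptive statistics with a 95% confidence interval for the mean. It names no survival method and no imputation method, whereas most other rows in that table name NRI or modified baseline observation carried forward (mBOCF).

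Elsewhere the plan treats permanent discontinuation as failure:

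- SAP 6.3 says that "NRI will be used when patients are permanently discontinued from study drug or otherwise have missing data". Protocol 10.3.1.1 has the same sentence. Where it stands, it is not limited to categorical variables.
- SAP 6.3.1 says that, under the composite strategy, patients whose intercurrent event leads to permanent discontinuation "are defined to have failed treatment for all subsequent time points".
- SAP Table AMBU.6.5 analyses symptomatic remission with NRI, and also as observed, at all scheduled visits.
- Protocol 7.7 counts use of prohibited UC medication for UC symptoms as treatment failure and requires such patients to come off study drug.

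SAP 4.2 points to Section 6.3 and Table AMBU.6.4 for the handling of intercurrent events.

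**The concern.** The censoring rule puts two kinds of child together. One completes induction without meeting the criterion and is censored near Week 12. That is ordinary administrative censoring and does no harm at Week 12. The other stops drug at, say, Week 4 because of worsening disease, an adverse event or prohibited UC medication, and is censored then.

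In a survival-type estimate, the second child leaves the risk set and is in effect given the later response chance of the children who stayed. In a mean that uses censored times as recorded, the same child contributes a short time, as if the outcome had been good. Either way, early failure improves the summary. Stopping during induction in active disease is plausibly informative, so this cannot be assumed to be neutral.

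The report could then show two results for the same children and the same stool-frequency and rectal-bleeding criterion: a by-visit remission rate that counts stoppers as failures, and a time-to-remission result that does not. The plan gives no reason for treating them differently.

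**Working it through.** The documents give no event rate, discontinuation rate or median for these endpoints, so there is no planned figure to reproduce. All counts below are assumptions that show direction and size. A group of 10 fits the SAP 5.2 target of about 10 children above 40 kg.

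**Formulas.** The product-limit rate by Week 12 is 1 − Π(1 − d/n), with d events and n at risk at each visit. The comparison rate keeps stoppers as non-events to Week 12, which gives responders/N.

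**Case A: 10 children, 2 respond at Week 8 and 2 at Week 12; k others stop after Week 4.**

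- k = 1: 1 − (7/9)(5/7) = 44.4%
- k = 2: 1 − (6/8)(4/6) = 50.0%
- k = 3: 1 − (5/7)(3/5) = 57.1%
- Stoppers kept to Week 12: 4/10 = 40%, whatever k is

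The product-limit median is Week 12 for k = 2 or 3. With stoppers kept in, it is not reached.

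**Case B: same group, 2 respond at Week 4 and 2 at Week 8; k others stop after Week 4.**

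- k = 1: 1 − (8/10)(5/7) = 42.9%
- k = 2: 1 − (8/10)(4/6) = 46.7%
- k = 3: 1 − (8/10)(3/5) = 52.0%
- Stoppers kept to Week 12: 40%

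If all four respond by Week 4, the difference is zero.

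**Mean time in Case A, under three readings of the planned mean.** The responders contribute 2×8 + 2×12 = 40 weeks.

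| Reading | k = 1 | k = 2 | k = 3 |
|---|---|---|---|
| Responders only, 40/4 | 10.0 | 10.0 | 10.0 |
| Censored times as recorded, (40 + 4k + 12(6 − k))/10 | 10.4 | 9.6 | 8.8 |
| All non-responders at Week 12, (40 + 72)/10 | 11.2 | 11.2 | 11.2 |

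Table AMBU.6.6 does not say which reading applies.

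**All 30 children, 15 responders (3, 4, 4, 4 at Weeks 2, 4, 8, 12).** Suppose five non-responders stop: 1 after Week 2, 2 after Week 4 and 2 after Week 8. Five is used as an upper range, borrowed from the gap between 30 enrolled and 25 PK-evaluable in SAP 5.2; it is not a stated discontinuation figure.

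- Product-limit rate: 1 − (27/30)(22/26)(16/20)(10/14) = 56.5%, against 15/30 = 50.0%. With 2 or 3 stops it is 52.0% or 53.8%.
- Mean time: responders only, 102/15 = 6.80 weeks; censored times as recorded, 248/30 = 8.27 weeks; all non-responders at Week 12, 282/30 = 9.40 weeks.

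With no early stops, the product-limit rate equals responders/N, and the second and third readings of the mean agree.

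**The case against.** A reader might infer that the censoring rule breaks the SAP's own composite rule outright. The documents do not support that. SAP 6.3.1 is written for categorical variables ("For analysis of categorical efficacy and health outcomes variables, missing data will be imputed using an NRI method") and is conditional: "The NRI method may be used when the estimand of interest uses the composite strategy". SAP 6.3 says that its methods "handle intercurrent events in different ways and thus are relevant to different estimands", and SAP 6.3.2 uses a while-on-treatment strategy for discontinuation other than for an adverse event. The censoring text in Table AMBU.6.4 can be read as the variable-specific rule. This objection stands as far as it goes. What remains is a departure from the failure rule used for the matching binary endpoint, and from the unrestricted NRI sentence in SAP 6.3, with no strategy named. The mBOCF rule does not supply one: carrying forward the baseline or last value would normally leave a child who has not yet responded a non-responder through Week 12.

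A reader might also infer that the trial will report a biased response curve. No Kaplan-Meier curve or cumulative rate is planned. The product-limit figures show what would happen if the censored times were used in that way. If the planned mean covers responders only, the censoring date has no effect. This stands too, and it exposes a companion gap: a plain mean has no defined way to use censored times.

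Three further limits stand. Time to first remission and remission at a visit measure different things, so some difference between them is expected even with no dropout. The mismatch with a binary NRI endpoint is visible only for remission, because Tables AMBU.6.5 and AMBU.6.6 show no by-visit row for symptomatic response. SAP 6.3.1 also fails patients who were not adequately assessed, so a change confined to discontinuers follows only part of that rule.

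**Conclusion.** The point holds as an unexplained inconsistency with a predictable direction. Children who permanently stop drug in induction without responding are censored at about the time they stop, and any summary that uses those times looks more favourable as more of them stop.

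In the assumed groups of 10 with 4 responders and 1 to 3 stops after Week 4, the Week 12 rate is about 3 to 17 percentage points too high (42.9% to 57.1% against 40%). In Case A, the mean is 0.8 to 2.4 weeks too short if censored times enter as recorded. For 30 children with 15 responders and 2 to 5 stops, the rate is about 2 to 7 points too high. These sizes rest on assumed counts and timing, because the documents give none.

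Importance is low. Both endpoints are exploratory, SAP 6.2 plans no treatment comparisons, and neither the PK primary objective nor the NRI-based secondary endpoints are affected. It would be wrong to infer that the dose decisions or the remission rates by visit are biased by this rule.

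**What to change.** In both rows of SAP Table AMBU.6.4, state that patients who permanently discontinue study drug during induction without meeting the criterion are carried as non-events to the end of the Induction Period (Week 12). Name this as the intercurrent-event strategy for the two variables. Say separately how children still on drug whose diary data end early are handled, since this change does not cover them.

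In SAP Table AMBU.6.6, replace the plain mean for both variables with a summary that handles censoring, such as the cumulative proportion by visit and the median, reported as not reached where that applies.

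The cost is a few sentences in the SAP and a small programming change, with no new data. The downside is that reported times and rates become slightly less favourable when children stop early; with no early stops, carrying them to Week 12 changes nothing.
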